## 2.2 DOSE RATIONALE

Transcranial magnetic stimulation (TMS) is a safe, non-invasive, widely-used tool that applies focal electric fields to the brain using magnetic coils placed on the scalp (Rossi et al. 2009). On the first stimulation session of the study, participants will receive a motor thresholding procedure in which electrodes are attached to the first dorsal interosseous muscle of the right hand, or another muscle on the hand or arm that is accessible to be targeted by TMS to the motor cortex. The contralateral motor cortex will be targeted by single pulses of TMS with increased stimulator output until a motor evoked potential (MEP) is generated: defined as a near-instantaneous increase muscle activity greater than 200 microvolts. Next, the intensity of single pulse TMS will be lowered until a MEP is generated on five out of ten pulses. This is defined as the participant's motor threshold (Rossi et al. 2009). If the motor threshold cannot be determined via MEP, the experimenter will use visible twitches as a proxy for MEP. Participants will receive TMS at 120% of their motor threshold. Each train consists of 5 pulses of TMS. Trains are delivered at individualized theta frequency, individualized alpha frequency, or one of two arrhythmic control conditions that matches for the duration of individual alpha frequency (IAF) and individual theta frequency (ITF) with randomized inter-pulse intervals. Thus, "arrhythmic-theta" refers to five TMS pulses with a random inter-pulse interval that lasts the same duration of the theta train of pulses, and "arrhythmic-alpha" refers to five TMS pulses

CONFIDENTIAL

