prefrontal cortex, and contrasted between a leftward and rightward retro-cue to derive the alpha frequency with peak amplitude in parietal cortex. These peak frequencies will be used for stimulation in the fourth and fifth session. In the third session, we will acquire a structural MRI and resting-state scan (10 minutes) for each participant. The resting-state functional MRI data will be analyzed using independent component analysis. This technique will identify regions in the anterior middle frontal gyrus and posterior intraparietal sulcus that are functionally connected within the frontal-parietal, "executive control," network. A previous meta-analysis of functional MRI studies found that the regions with peak retro-cue activity was at Montreal Neurological Institute coordinates (-40, 36, 28) for anterior middle frontal gyrus and (-38, -48, 44) for inferior intraparietal sulcus. Therefore, we will constrain our search lights to the anatomical landmarks and these coordinates. The center of mass in these regions will be used for targeting

CONFIDENTIAL

with TMS in the subsequent fourth and fifth sessions. In the fourth and fifth sessions, stimulation will be delivered at the timing relative to retro-cue, frequency, and spatial location based on our previous localizers. During stimulation, the location of the TMS coil needs to be aligned to the targeted brain region with neuro-navigation software that records the accuracy of each TMS pulse relative to the target (Localite, Sankt Augustin, Germany). On each trial, the stimulation type will be randomly selected, counter-balanced, and inter-mixed (see section 4.1 below). The effects of rhythmic TMS are not expected to last for more than a few cycles beyond stimulation itself (Thut et al. 2011; Hanslmayr et al. 2014; Albouy et al. 2017). Therefore, the experimental design randomly intermixes the stimulation type within every task block.

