### 11.1 STATISTICAL ANALYSIS STRATEGIES

The statistical analysis plan below aligns with the aims that are described in Section 2.3. all statistical estimates of population parameters will be tabulated along with corresponding confidence intervals (CIs) to convey levels of precision / imprecision. All hypothesis tests that yield large p-values ( $p>0.05$ ) will be reported as being inconclusive.

*Phase One* overarching goal: Investigate the causal role of frontal theta and parietal alpha oscillations in the prioritization and suppression of working memory representations. To control for non-specific effects of rhythmic TMS, we will use an active control: arrhythmic TMS (randomized inter-pulse-interval) that is matched to the target stimulation in number of pulses and temporal duration. All analyses will be performed on the difference from condition-matched arrhythmic TMS. The key analyses are built upon a three-way parallel arms design: with factors TMS frequency (theta versus alpha), location (frontal versus parietal), and cue direction (left versus right retro-cue). There is an equal number of trials for each of these conditions and there are 75 trials for each condition per participant.

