Aim 2 (primary outcome): Stimulation is hypothesized to increase the targeted frequency of stimulation relative to arrhythmic stimulation. This aim will provide evidence of target engagement, i.e. that stimulation is effective at modulating the targeted rhythm. Using Morlet wavelet convolution, the amplitude of theta and alpha oscillations will be estimated during task performance. The average across trials for each conditions will be calculated and baseline corrected using decibels to the time before the encoding array (700 to 300 milliseconds). Then, the average amplitude within the individual theta (ITF  $+$ /- 1 Hz) and alpha frequency (IAF  $+$ /- 1 Hz) band will be calculated for the second half of the train of TMS pulses. Previous research has shown that amplitude increase from stimulation increases over the course of the TMS train. Frontal-theta and parietal-alpha amplitude values will be submitted to a two-way repeated-measures ANOVA with TMS frequency by TMS site. We hypothesize to find a significant interaction ( $p < 0.05$ ) between TMS site and TMS frequency such that theta amplitude in frontal cortex increases greater for TMS to frontal in theta frequency and alpha amplitude in parietal cortex increases greater for TMS to parietal cortex in alpha frequency. Post-hoc t-tests will be performed using Tukey's method to control for multiple comparisons. *Sensitivity analysis*: To understand the specificity of this effect, the time-course for the impact of stimulation of amplitude will be plotted as well as the topographic plot for our effects. Cluster analysis will be used to estimate the spread of our effect in time and space. These analyses provide evidence to the robustness of the

impact of stimulation on amplitude.

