**Aim 5 (secondary outcome):** Stimulation that is aligned to the endogenous activity of the brain is hypothesized to entrain neural activity. Inter-trial phase coherence (ITPC) quantifies alignment of neural oscillations across trials. Stimulation in frontal-theta and parietal-alpha is proposed to increase ITPC in a frequency specific manner relative to control stimulation. A similar method for extracting instantaneous phase is used as that used to extract instantaneous amplitude (Aim 2). ITPC is calculated as the average phase angle in complex space of unit vectors across trials, then taking the magnitude of the resulting vector. These ITPC values are then averaged for the second half of the TMS train as described in (Aim 2). Frontal-theta and parietal-alpha ITPC values will be submitted to a two-way repeated-measures ANOVA with TMS frequency by TMS site. We hypothesize to find a significant interaction ( $p < 0.05$ ) between TMS site and TMS frequency such that theta ITPC in frontal cortex increases greater for TMS to frontal in theta frequency and alpha ITPC in parietal cortex increases greater for TMS to parietal cortex in alpha frequency. Post-hoc t-tests will be performed using Tukey's method to control for multiple comparisons. *Sensitivity analysis:* Similar to the sensitivity analysis of Aim 2, the time-course and topographic plots with cluster analysis will quantify the spread of these effects.

**Phase Two Overarching Goal:** Investigate the causal role of in-phase theta-frequency between frontal and parietal cortex in the prioritization and suppression of working memory representations. To control for non-specific effects of dual-site rhythmic TMS, we will use an active control: arrhythmic TMS (randomized inter-pulse-interval). Two

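### Aims 2 and 5 are tested only within the pulse train, where periodic pulse-evoked responses can inflate ITPC, and sometimes amplitude, without any change in the ongoing rhythm

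*Combined protocol and SAP*

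**What the plan says.** Section 11.1 sets one window for both outcomes. For Aim 2 (primary), wavelet amplitude within 1 Hz of the individual theta or alpha frequency "will be calculated for the second half of the train of TMS pulses". For Aim 5 (secondary), "These ITPC values are then averaged for the second half of the TMS train". The stated reason for the window, given under Aim 2, is that earlier work saw the amplitude effect grow during the train.

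The control is arrhythmic TMS, "matched to the target stimulation in number of pulses and temporal duration", and "All analyses will be performed on the difference from condition-matched arrhythmic TMS". Its inter-pulse intervals are random (Section 2.2). Each outcome goes into an ANOVA of TMS frequency by TMS site, and the interaction is the named test.

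Of Aim 2 the plan says: "This aim will provide evidence of target engagement, i.e. that stimulation is effective at modulating the targeted rhythm". Aim 5 is framed as entrainment. The sensitivity analyses for both aims are time-course plots, topographies and a cluster analysis. No post-train window is named, and no step removes or models the response to the pulses. On persistence, Section 4 says: "The effects of rhythmic TMS are not expected to last for more than a few cycles beyond stimulation itself".

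**The concern.** A rhythmic train differs from its arrhythmic control in two ways. It may engage an ongoing oscillation, and it certainly delivers pulses at regular intervals. A response evoked by each pulse, whether cortical, somatosensory or auditory, recurs at the analysed frequency and at fixed latency in the rhythmic condition only. Subtracting the arrhythmic condition removes effects of pulse count and train length, but not this periodicity.

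ITPC measures phase alignment across trials, so it is the more exposed measure. The interaction does not settle the matter either: a response that is largest under the coil and recurs at the pulse rate gives the pattern that both aims predict.

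At stake is what a positive result means. Aim 2 supplies the mechanistic support for reading a behavioural effect in Aim 1 as an effect of theta or alpha oscillations. As written, significance could be reported as modulation or entrainment of the brain's own rhythm when a stimulus-locked response would explain it.

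**Working it through.** **The plan's own figures.** Section 11.2 gives 21 participants for an alpha amplitude effect of 0.83, 44 for a theta effect of 0.56 and 48 for the behavioural effect of 0.532. A two-sided paired t-test at 0.05 with 95% power returns 21, 44 and 48 exactly. These figures say how many participants detect a difference, not what causes it, so they do not bear on this point.

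**Inputs from the protocol.**
- Section 2.2: "Each train consists of 5 pulses of TMS". The minimum inter-pulse interval is 20 ms, and arrhythmic trains last as long as the rhythmic ones.
- Section 6.2: spacing is 200 ms for theta and about 100 ms for alpha. A train spans 4 intervals, so 4 x 200 = 800 ms or 4 x 100 = 400 ms. The window is 400-800 ms or 200-400 ms.
- Section 11.1: 75 trials per condition. Section 6.5.2: a two-second delay.

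**Step 1, the mechanism by hand.** With linear superposition, the evoked part at frequency f is E(f) x S, where S is the sum over the five pulses of exp(-i2πfτ) and τ is pulse time.
- Rhythmic: τ = 0, 1/f, ..., 4/f. Every term is 1, so S = 5 with the same phase on every trial.
- Arrhythmic: the first and last pulses are fixed by the matched duration and contribute 2. If the three inner pulses fall uniformly over the four cycles, their mean contribution is 0. The cross-trial mean of S is then 2 and its root mean square is √(2² + 3) = 2.65. Imposing the 20 ms minimum numerically lowers the mean to about 1.9 at 5 Hz and 1.7 at 10 Hz.

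The part of the evoked response that is consistent across trials is therefore about 5 against 2, and the subtraction leaves the difference. This is for the whole train at exactly f. A short wavelet over half the train also picks up neighbouring frequencies, so amplitude need not follow the same ratio.

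**Step 2, simulation with zero entrainment.** Pink noise plus an ongoing random-phase rhythm that stimulation never changes, plus a fixed waveform per pulse. Assumptions not in the documents: three waveforms (short, N100-like, single-peaked), peaks of 1 or 2 noise SD, and wavelets of 3 or 5 cycles. At 5 and 10 Hz this gives 3 x 2 x 2 x 2 = 24 settings.

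| Rhythmic minus arrhythmic | ITPC | Amplitude |
|---|---|---|
| In-train window | +0.05 to +0.81 (24 of 24 raised) | +0.2 to +3.0 dB in 17; -0.48 to +0.15 dB in 7 |
| Post-train window | -0.02 to +0.04 | -0.14 to +0.17 dB |
| In-train, no evoked response | about 0.01 | about 0.02 dB |

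A separate simulation at the same peak sizes gave in-train ITPC differences of +0.05 to +0.77, and amplitude from about 0 to +3.1 dB, small for peaks below 1 SD.

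**Step 3, the interaction.** For frontal theta, with n = 48, a 4-cycle wavelet, a peak of 1 SD and site taken as a within-participant factor:

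Interaction = [Δ(frontal, theta) - Δ(frontal, alpha)] - [Δ(parietal, theta) - Δ(parietal, alpha)]

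where Δ is rhythmic minus arrhythmic. Spread is the assumed evoked size at the frontal sensor when the parietal site is stimulated.

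| Waveform, spread | Amplitude | ITPC | Post-train amplitude | Post-train ITPC |
|---|---|---|---|---|
| N100-like, 0.3 | +3.26 dB | +0.53 | +0.25 dB | +0.043 |
| N100-like, 0.6 | +2.06 dB | +0.27 | -0.14 dB | -0.029 |
| Single-peaked, 0.3 | +0.81 dB | +0.20 | +0.04 dB | 0.000 |
| Single-peaked, 0.6 | +0.57 dB | +0.16 | -0.08 dB | +0.004 |

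All in-train p-values are about 0.001 or smaller for amplitude and below 1e-9 for ITPC. The post-train window here was 1.5-3.5 cycles after the last pulse. Its two N100-like ITPC values reached p = 0.011 and 0.049 with opposite signs. They are small, but the window start needs its own overlap check.

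**Step 4, can a later window tell the explanations apart?** At 5 Hz, an evoked response alone gave +1.3 dB and +0.55 in-train, and -0.17 dB and 0.00 post-train. Entrainment alone, built to last four cycles past the train, gave +2.0 dB and +0.82 in-train, and +2.6 dB and +0.85 post-train. Only the later window separates them.

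**Step 5, is there room?** Three cycles after the last pulse end at 800 + 600 = 1,400 ms from train onset at 5 Hz, 400 + 300 = 700 ms at 10 Hz, and 1,000 + 750 = 1,750 ms at 4 Hz, the slowest theta. All fit in two seconds, but at 4 Hz only if the train starts within 250 ms of the delay. The protocol gives no numerical train onset.

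**The case against.** Five counter-arguments deserve weight.

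- **Amplitude inflation is conditional.** A reader might infer that superposition always raises amplitude. It does not: 7 of 24 settings were near zero or negative. With five other waveforms the in-train difference was -0.26 to +0.42 dB at peaks of 0.25-1 SD and -0.05 to +1.44 dB at 2 SD. This stands, and for Aim 2 the right wording is that amplitude can be inflated.
- **The plan already looks beyond the train.** The time-course and cluster analyses may extend past it, and Aim 3 applies the same method to the mismatched site and band pairs, where superposition would also act. These are relevant data. But they are presented as spread, robustness or a separate hypothesis, with no post-train test and no rule linking them to the reading of Aims 2 and 5.
- **Aim 2 concerns an online effect and does not use the word entrainment.** True, and the in-train window has a stated rationale. But growth over the train is also what overlapping responses to successive pulses give, so it does not discriminate.
- **A post-train criterion could reject a real effect.** Section 4 sets an upper limit on persistence, not a minimum. When true phase alignment was simulated with a decay constant of one cycle or less, the ITPC difference was +0.42 to +0.46 in-train but -0.01 to +0.03 at 1.5-3 cycles after the last pulse. This stands and rules out a hard gate.
- **White noise is played during stimulation (Section 5.2).** It addresses auditory responses, not cortical or somatosensory ones.

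**Conclusion.** The concern holds as a limit on interpretation. A significant in-train result for Aim 2 or Aim 5 shows a stimulus-locked response at the stimulated frequency, more than arrhythmic pulses produce. By itself it does not show that the endogenous rhythm was modulated or entrained. The case is strongest for ITPC, which rose in every simulated setting, and conditional for amplitude. The interaction does not exclude the rival explanation when the evoked response is largest at the stimulated site. This was simulated for frontal theta only; parietal alpha rests on the same reasoning. It is a shift in means, so making site a between-participant factor would not remove it.

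The documents give no evoked amplitude, waveform or wavelet width, so direction is the finding and the decibel and ITPC values are illustrations. Two stronger readings are not supported. A reader might set simulated standardised differences against the planning effects of 0.56 and 0.83, but the simulated variance between participants is itself assumed. A reader might also conclude that a positive result would be an artefact, but the plan does not show that; it only lacks a way to tell.

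**What to change.** Keep the in-train ANOVA as the named test in both aims, and add to Section 11.1:

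1. At least one supportive analysis, fixed before the data are examined: (a) the same ANOVA on a post-train window clear of evoked-response and wavelet overlap, for example 1.5-3 cycles after the last pulse, set against the actual train onset and ending before the probe; and/or (b) the in-train ANOVA after subtracting the superposed single-pulse response estimated from the arrhythmic trials. For (a), state the wavelet width and check the overlap. With 4 cycles the wavelet SD is 4/(2π) = 0.64 cycles, so a start at 1.5 cycles lies 1.5/0.64 = 2.4 SD after the last pulse, before the duration of the evoked response is counted.
2. A rule for wording: in-train significance alone is reported as a stimulus-locked response at the stimulated frequency. Modulation or entrainment of the endogenous rhythm is claimed only with support from (a) or (b).
3. A statement that a null post-train result is inconclusive and is not evidence against an online effect. This agrees with the plan's general rule of reporting p > 0.05 as inconclusive.

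The cost is SAP text and further analysis of EEG already being recorded. The post-train test will have less power because any after-effect is brief, and (b) assumes that responses to successive pulses add linearly.

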**Aim 3 (secondary outcome):** Theta and alpha oscillations are hypothesized to play antagonistic roles whereby theta oscillations are associated with an increase in neural excitability and alpha oscillations are associated with a decrease in neural excitability. Therefore, we will investigate the impact of stimulation on the other frequency band. Theta stimulation is hypothesized to decrease the amplitude of alpha oscillations and alpha stimulation is hypothesized to decrease theta oscillations. This method is identical for that of Aim 2 except that the values submitted to the ANOVA are instead frontal-alpha and parietal-theta amplitude values. We hypothesize to find a significant interaction ( $p < 0.05$ ) between TMS site and TMS frequency such that alpha amplitude decrease is greater for TMS to frontal in theta frequency and theta amplitude decrease is greater for TMS to parietal cortex in alpha frequency. Post-hoc t-tests will be performed using Tukey's method to control for multiple comparisons. *Sensitivity analysis:* Similar to the sensitivity analysis of Aim 2, the time-course and topographic plots with cluster analysis will quantify the spread of these effects. Furthermore, an exploratory theta-alpha antagonism metric (theta amplitude minus alpha amplitude within the site of interest) will be used to quantify a shift in the relative distribution of theta and alpha amplitude.

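### Aim 2 (primary) claims a rise over arrhythmic TMS, but its only criterion is a site-by-frequency interaction that can be met with no rise in either targeted rhythm

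*Combined protocol and SAP*

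**What the plan says.** All references are to the combined protocol and SAP.

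- **Claim (Section 11.1, Aim 2, primary).** "Stimulation is hypothesized to increase the targeted frequency of stimulation relative to arrhythmic stimulation". The plan presents this as its evidence of target engagement.
- **Scale (Section 11.1, Phase One).** "All analyses will be performed on the difference from condition-matched arrhythmic TMS". Zero therefore means no effect of rhythm.
- **Test (Aim 2).** "Frontal-theta and parietal-alpha amplitude values will be submitted to a two-way repeated-measures ANOVA with TMS frequency by TMS site". The criterion is an interaction at p < 0.05, and its direction is worded relatively: "theta amplitude in frontal cortex increases greater for TMS to frontal in theta frequency", with a parallel statement for parietal alpha. Follow-up is by Tukey-adjusted t-tests. The sensitivity analyses are time courses, topographies and cluster analysis.
- **Estimation (Section 11.1, opening).** "all statistical estimates of population parameters will be tabulated along with corresponding confidence intervals". No conclusion is tied to these intervals.
- **Sample size (Section 11.2).** The EEG justification uses rhythmic versus arrhythmic TMS: effect 0.83 for alpha (21 participants) and 0.56 for theta (44 participants), each for 95% power.
- **Aim 3 (secondary).** The general hypothesis is "Theta stimulation is hypothesized to decrease the amplitude of alpha oscillations and alpha stimulation is hypothesized to decrease theta oscillations". The operational prediction is narrower: "alpha amplitude decrease is greater for TMS to frontal in theta frequency", with the mirror statement for parietal theta under parietal alpha TMS. On method: "This method is identical for that of Aim 2 except that the values submitted to the ANOVA are instead frontal-alpha and parietal-theta amplitude values".

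**The concern.** An interaction compares cells with one another, whereas an increase over arrhythmic TMS is a statement about a cell and zero. The interaction can be positive because the matched cells rose, because the mismatched cells fell, or both. Tukey follow-up does not separate these cases, since it too compares cell with cell.

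The fall is not far-fetched, because Aim 3's general sentence predicts that stimulating in one band lowers the other. If that happens at the stimulated site and matched stimulation does nothing, Aim 2's criterion can still be met. The trial's evidence of target engagement would then rest on suppression, and the plan does not say what should be concluded.

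**Working it through.** **1. The plan's own figures.** A one-sample t-test (noncentral t, two-sided 0.05, 95% power) gives n = 21 for effect 0.83 (power 0.951) and n = 44 for effect 0.56 (power 0.953). Both stated numbers reproduce. They size a test of a matched cell against zero, which Aim 2 does not contain.

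**2. The contrast in one combined ANOVA.** Let FT and FA be frontal theta under frontal theta and frontal alpha TMS. Let PT and PA be parietal alpha under parietal theta and parietal alpha TMS. All are differences from arrhythmic TMS. The matched cells are FT and PA.

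Interaction = FT − FA − PT + PA

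- True rise of d in both matched cells, others zero: d − 0 − 0 + d = 2d.
- No matched rise, suppression d in both mismatched cells: 0 + d + d + 0 = 2d.

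The test cannot tell these apart.

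**3. Dependence on the reading.** Aim 2 does not say whether one combined ANOVA or one per band is meant. With no matched rise:

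| Reading and pattern | Contrast |
|---|---|
| Combined; suppression in both mismatched cells | 2d |
| One ANOVA per band; suppression only at the stimulated site | d in each |
| One ANOVA per band; equal suppression from both sites | 0 |
| Aim 3's site-specific pattern (frontal alpha, parietal theta fall) | 0, as neither outcome is an Aim 2 cell |

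Where the contrast is 0, the chance of significance in the predicted direction is the nominal 2.5%.

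**4. Illustrative size.** Assumptions, none of them in the documents: cell SD 1, no matched rise, d = 0.3 or 0.5, common correlation ρ between cells. *Crossed* means that all 48 receive both sites; *parallel* means 24 per site.

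- Crossed, combined: noncentrality = 2d√48 / √(4(1−ρ)), 47 df. For d = 0.5, ρ = 0: 6.93/2 = 3.46, power 0.924.
- Parallel, combined: noncentrality = 2d / √(4(1−ρ)/24), 46 df. For d = 0.5, ρ = 0: 1/0.408 = 2.45, power 0.669.

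| Combined ANOVA | ρ = 0 | 0.3 | 0.5 | 0.7 |
|---|---|---|---|---|
| Crossed, d = 0.3 | 0.530 | 0.682 | 0.821 | 0.960 |
| Crossed, d = 0.5 | 0.924 | 0.982 | 0.998 | 1.000 |
| Parallel, d = 0.3 | 0.301 | 0.405 | 0.530 | 0.748 |
| Parallel, d = 0.5 | 0.669 | 0.818 | 0.924 | 0.992 |

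Per band with local suppression, the contrast is d. At ρ = 0 a single ANOVA is significant in 17% (d = 0.3) to 40% (d = 0.5) crossed, or 11% to 22% parallel. Aim 2 predicts both the theta and the alpha pattern. If both must be met and the two contrasts are independent, squaring gives about 3% to 16% crossed, or 1% to 5% parallel.

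**5. The opposite error.** If all cells rise without frequency specificity (frontal 0.56, parietal 0.83), the interaction is significant in the predicted direction in only about 2.5% of simulated trials. Neither the interaction nor the zero tests alone can carry a claim of specific engagement.

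**6. Power of the zero tests at the cited effects.** With n = 48: theta 0.967, alpha 0.9999, both 0.967 × 0.9999 = 0.967. With an assumed 24 per site: 0.748 × 0.973 = 0.728.

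**The case against.** The strongest reply is that the plan already contains most of what is needed. Values are arrhythmic-corrected, a direction is stated, and estimates come with confidence intervals. If cell means are tabulated, a matched cell at zero would be visible. Section 11.2 shows that the rhythmic-versus-arrhythmic comparison was intended, and this is a mechanistic pilot in healthy adults. All of that stands. It makes the gap one of decision rule rather than of data or design, but it does not supply the rule.

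It is also fair that the problem needs particular conditions. Aim 3's site-specific prediction moves none of Aim 2's four cells. A reader might infer that the plan's own Aim 3 prediction would by itself produce a false pass on Aim 2, but only its general sentence does so, and only under some ANOVA readings. A reader might also take a figure such as 92% as Aim 2's false-positive rate. The documents do not support that: they give no suppression size, SD or correlation, and the figure belongs to one reading with d = 0.5 and independent cells.

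Finally, requiring both rhythms to rise before anything is claimed would be stricter than necessary. Separate claims by rhythm are legitimate if multiplicity is handled.

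**Conclusion.** The concern holds in limited form. Aim 2's stated criterion does not establish its stated claim, because a significant interaction is compatible with no rise in either targeted rhythm. This is algebra and needs no assumed effect size.

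How often it would mislead depends on the reading: from not at all (contrast 0) to 53-100% crossed or 30-99% parallel for the combined ANOVA, under the assumptions in step 4. The per-band reading lies between. These are illustrations, not estimates for this trial.

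It would be wrong to infer that the EEG data are invalid or that the trial cannot show target engagement; the required comparison can be made from data already scheduled. Secondary Aims 3 and 5 share the gap. Aim 3 claims a decrease and Aim 5 a rise in ITPC relative to control stimulation, and each rests on the same kind of interaction.

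**What to change.** In Section 11.1, Aim 2:

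- Test each arrhythmic-corrected matched cell against zero, two-sided 0.05, with its confidence interval: frontal theta under frontal theta TMS, and parietal alpha under parietal alpha TMS.
- Claim an increase only for a rhythm whose test is positive, and report the other as inconclusive. If the two rhythms are claimed separately, control multiplicity over the two tests (for example Holm). No adjustment is needed if the overall engagement claim requires both.
- Keep the interaction as the specificity test and state whether it is one combined ANOVA or one per band.
- State that frequency- and site-specific engagement needs both the positive zero tests and the interaction. A positive zero test without the interaction is reported as a non-specific increase.

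Apply the same rule to Aim 3 (frontal alpha under frontal theta TMS, and parietal theta under parietal alpha TMS, below zero) and Aim 5 (matched ITPC cells above zero). Section 11.2 gives no power for the Aim 3 tests, and the plan should say so.

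**Cost.** A few one-sample tests and sentences, with no added visits. The real cost is power. Requiring both Aim 2 tests, unadjusted, gives 96.7% with 48 participants in each cell but about 73% with 24 per site. The parallel-arms text (Section 1.5, version 7.0, and Section 11.1, Phase One) and the within-participant site factor in Aim 1 must therefore be reconciled, and the applicable power stated.

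The documents do not say whether data collection is complete. If it is, the change must be dated and disclosed as post hoc, because Section 4.1 says that the study is not blinded.
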